Also addressing to the new national healthcare system number 27, 2014 regarding Technical Instructions System of Indonesian Case Base Groups, where medical coverage is not based on medical expenses but the grouping of diagnoses and treatment based on ICD-9, the high cost of medical products often complicate the hospital policy.¹¹

Therefore, as suggested by the Indonesian Ministry of Health, we are going to use our local plate and screw for maxillofacial fractures management to answer the balance of supply and demand of local medical products. On the other hand, it could help the government to reduce medical expenses.

Aim Of The Study

The aim of this experiment is to investigate the usage of the locally-made miniplate and screw are not inferior compared to the existing benchmark miniplate and screw in terms of bone healing, surrounding tissue reactions, and screw loosening.

Study Hypothesis

The locally-made miniplate and screw are not-inferior compared to the existing benchmark miniplate and screw in terms of bone healing, surrounding tissue reactions, and screw loosening.

OBJECTIVES AND OUTCOMES

Primary Objective

To evaluate bone density radiologically (in Houndsfield Unit) after plate and screw fixation with locally-made compared to existing benchmark miniplate and screw

Secondary Objective

- To evaluate if there is any loosening screw following both locally-made and existing benchmark miniplate and screw fixation.
- To evaluate if there is any sign of local tissue reaction following both locally- made and existing benchmark miniplate and screw fixation.

STUDY DESCRIPTION

Research Design

This study will be performed on patients with maxillofacial fractures. The study is a blind randomized clinical study comparing locally-made titanium plate and screws with the existing benchmark, BIOMET® miniplate, and screw. After fixation, bone density, local tissue reactions, and screw loosening between these two devices at specific periods will be compared.

Time And Place

The clinical study will be conducted at Cipto Mangunkusumo Hospital, Jakarta, Indonesia from September 2019 – April 2020. Surgery will take place at Cleft Craniofacial Center Operating Theatre. It will be conducted by two consultants of craniomaxillofacial surgeons.

STUDY POPULATION

Inclusion Criteria

- Midface fracture with the indication of surgery
- Midface fracture sustained within 2 weeks

Exclusion Criteria

- Comminuted and defect fracture

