- Midface fracture on patients with systemic diseases affecting bone healing.
- Midface fracture in children
- Midface fracture in multiple trauma patients with neurological deterioration

Dropout Criteria

- Patient who is unable to complete radiological evaluation after surgery due to lost to follow up or refuse to continue the evaluation will be replaced by another sample
- Patient with signs of bacterial infection either locally or systemically or implant failure are not dropouts, their last data of observation will be included and analyzed (Last-Observation-Carried-Forward (LOCF) method).

METHODOLOGY

Subject Allocation

Subject is the fracture line found on the patient. The surgeon is not blinded on which miniplate is going to use because the miniplate has different characteristic.

Intervention

Pre-operatively

- Patients will sign the informed consent sheet and declare that they want to be enrolled as subjects and obey all the instructions given postoperatively
- The patients will shower with chlorhexidine 4% 27 soap 1 day before surgery
- An empiric antibiotic will be administered 1 hour preoperatively: intravenous injection of Ampicillin Sulbactam 1.5 gr/IV 28 to prevent postoperative infection.

Intra-operatively

- All patients will be treated under general anesthesia.
- After induction of anesthesia, the operating field is disinfected with povidone-iodine
- Draping the patient, exposing only the area of surgery
- Local anesthetic solution with a vasoconstrictor is administered along the incision line area for homeostasis
- Maxillary mandibular fixation is performed to maintain the occlusion
- Midface fracture site approach through an intra-oral or extra-oral incision according to the accessibility at that time and may differ for every patient
- The fractured segment is reduced into proper position using Carroll-Girrard, hook, elevator or Rowe disimpaction forceps.

- The surgeon will received a seal envelope contain an instruction to use locally-made miniplate or existing benchmark miniplate and then it will be bend as desired based on the fracture site contour
- The surgeon will place the miniplate on the fracture site based on AO/CMF point fixation sequence.
- The plate is tapped manually with gentle pressure. The screw is inserted into the hole using a screwdriver and held parallel to the long axis of the drill hole.

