- The steps of drilling, tapping and screwing all panel holes are repeated for all screw holes followed by the closure of the incision with usual manner.
- The maxillary mandibular fixation is removed and the jaw is manipulated to evaluate the occlusion and also measure the maximal mouth opening. Forced-duction test is performed when there is a placement of the plate on the orbital rim.
- The maxillary mandibular fixation is maintained for approximately 2 weeks and evaluates once a week during patient visit to the outpatient clinic

Post-operatively

- Intravenous injection of Ampicillin Sulbactam 1.5 gr every 6 hours is given for 1-2 days, then when the patient is discharged it is replaced by Amoxicillin/clavulanic acid 625 mg orally every 8 hours for another 7 days post-operatively
- Intravenous injection of Paracetamol 1 gr every 8 hours is given for 2 days followed by oral tablets 500 mg every 8 hours as needed for another 7 days for pain control
- All patients undergo a non-contrast head CT scan on day one postop as a baseline
- All patients are discharged two days after surgery and instructed to have liquid diet for 2 weeks post-operatively
- Patients will visit the outpatient clinic once a week for 3 weeks. Sign of bacterial infection or local tissue reaction will evaluate by the end of 3rd week
- All patients performed a non-contrast head CT scan at 3 months postoperatively.

Miniplate And Screw Placement

Once a patient lies down on the operating table under general anesthesia, the surgeon will identify the fracture segment. The surgeon will received a seal envelope contain an instruction to use locally-made miniplate or existing benchmark miniplate to be placed on the fracture site according to a predetermined randomization list. The decision where to place the locally made miniplate or existing benchmark miniplate depends on AO/CMF point of fixation sequence.

Assessing Study Results

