After completing the procedure, subjects will undergo non-contrast head CT scan evaluation immediately after surgery as a baseline, and by the end of 3rd months post-operation. Afterward, a radiologist consultant as a blinded independent evaluator will assess the bone density score in each subject. A score sheet will be given to the assessor. Subjects will also be instructed to visit the outpatient clinic once a week for 3 weeks post-operatively to evaluate their appearances clinically if there is any sign of bacterial infection or local tissue reaction that will be taken care of by consultants of craniomaxillofacial surgeons.

Bone Density

Bone density of each subject will be recorded in Hounsfield Unit (HU). The bone density score of each subject will be noted and scores between the two brands will be compared. The scores will be evaluated by a radiologist consultant and act as an independent evaluator after the subject has completed all their Head CT evaluation.^{29, 30}

[figure not shown]
Screw Loosening

Screw loosening will be recorded, whether it is present or not. It will be evaluated by a radiologist consultant after the subject completed all their Head CT evaluation.

Tissue reaction

Local tissue reactions such as edema, bacterial infection, or any other signs of the inflammation process, will be recorded by the end of the 3rd week during patient's visit outpatient clinic. It will be evaluated by consultants of craniomaxillofacial surgeons and.

Research Protocol

DATA ANALYSIS AND DATA PRESENTATION

Data on bone density are quantitative, all scores from points of evaluation group will be collected, and scores for the dependent variables between groups will be statistically compared using independent t-test or Mann Whitney test depending on the distribution of the data is normal or not. Other findings will be presented using descriptive statistics.

Table 2. Dummy table of bone density (HU) in group I (Locally-made miniplate and screw) versus group II (existing benchmark miniplate and screw) at different observation periods.

Time (Postop)	Group I (Mean ±SD)	Group II (Mean ±SD)	p-Value*
Bone Density			
Immediately post op			
Three months post op			

*Statistically significant difference versus baseline reading if p-value ≤ 0.05 HU=Hounsfield unit.

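### The Aim and Hypothesis claim non-inferiority on tissue reactions and screw loosening, but the plan only describes these two outcomes, and no margin for either appears in the text available

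*Combined protocol and SAP*

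**What the plan says.** All references are to the combined protocol and SAP.

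- **Aim Of The Study:** the local devices "are not inferior compared to the existing benchmark miniplate and screw in terms of bone healing, surrounding tissue reactions, and screw loosening". The same claim on the same three outcomes is repeated under **Study Hypothesis**.
- **Secondary Objective:** the wording is purely descriptive: "To evaluate if there is any loosening screw" and "To evaluate if there is any sign of local tissue reaction", after either type of plate.
- **Data Analysis and Data Presentation:** bone density gets a between-group t-test or Mann-Whitney test. For everything else, "Other findings will be presented using descriptive statistics".
- **Table 3 (dummy):** tissue reaction and screw loosening, with one column for each group of 60. There is no column for a difference, interval or p-value. The later loosening row is labelled 2 months, whereas Post-operatively, Assessing Study Results and Table 2 all place the late CT or its reading at 3 months.
- **Subject Allocation:** "Subject is the fracture line found on the patient". **Miniplate And Screw Placement** adds: "The decision where to place the locally made miniplate or existing benchmark miniplate depends on AO/CMF point of fixation sequence".
- **Tissue reaction:** the outcome covers "Local tissue reactions such as edema, bacterial infection, or any other signs of the inflammation process" and is recorded at a clinic visit by the end of week 3.

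The text available for review gives no margin for tissue reaction or loosening.

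**The concern.** A non-inferiority claim says that an unacceptable excess has been ruled out. That takes an estimate of the difference, its uncertainty, and a limit to compare it with. For tissue reaction and loosening the planned output is a count per group, which rules out nothing by itself. The likely misstep is to see similar counts and report that the hypothesis was confirmed.

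The introduction presents the study as support for using a local implant in place of an imported one, and these are the two outcomes that speak to how the implant is tolerated and whether it holds. A reader could work out a crude interval from Table 3, but not one that allows for several fracture lines in one patient, because the table does not give the number of patients.

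**Working it through.** **1. Claim against analysis**

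| Outcome | Aim and Hypothesis | Formal objective | Planned analysis | Margin in available text |
|---|---|---|---|---|
| Bone density (bone healing) | Non-inferior | Primary: evaluate and compare | t-test or Mann-Whitney | None |
| Tissue reaction | Non-inferior | Secondary: is there any? | Descriptive | None |
| Screw loosening | Non-inferior | Secondary: is there any? | Descriptive | None |

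For the last two rows, objective, analysis and table agree with each other. Only the Aim and Hypothesis go further.

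**2. What counts leave open**

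The plan states no figure for these outcomes that could be reproduced, and the 60 per group in Table 3 has no derivation in the available text. The following is therefore an illustration. Its inputs are n = 60 lines per group (Table 3), z = 1.96, and assumed event counts. Lines are first treated as independent.

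Wilson limits for one group with proportion p:

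(p + z²/2n ± z·√[p(1−p)/n + z²/4n²]) / (1 + z²/n)

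With limits l and u, the Newcombe interval for equal observed proportions is ±√[(u − p)² + (p − l)²].

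- *0 v 0:* l = 0 and u = 3.84/(60 + 3.84) = 0.0602. The interval is ±√(0.0602² + 0) = **±6.0 points**.
- *3 v 3:* p = 0.05, l = 0.0171, u = 0.1370. The interval is ±√(0.0870² + 0.0329²) = **±9.3 points**.
- *12 v 12:* ±14.3 points. *18 v 18:* ±16.1 points. These higher counts are shown because the tissue-reaction definition includes edema and any inflammatory sign.

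**3. Chance of ruling out an excess**

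This is an exact binomial enumeration of the probability that the upper Newcombe limit lies below an assumed margin, with equal true rates and 60 independent lines per group:

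| True rate (assumed) | 10-point margin | 5-point margin |
|---|---|---|
| 2% | 83% | 25% |
| 5% | 58% | 18% |
| 20% | 28% | 10% |
| 30% | 23% | 9% |

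At low rates the Newcombe interval is conservative: the same enumeration gives coverage of 99.6% at 2% and 97.3% at 5%. A normal approximation is more favourable for the 10-point margin, with 97.5% and 71.0% at those rates. The low-rate entries therefore depend on the method.

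**4. Clustering of lines within patients**

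Assume two lines per patient and an intraclass correlation (ICC) of 0.1 to 0.5, and replace n by n divided by the design effect.

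- Both lines on the same plate type: design effect 1 + ICC, so n becomes 60/1.1 = 54.5 down to 60/1.5 = 40. The 3 v 3 interval becomes ±9.9 to ±12.1.
- One line on each plate type: design effect 1 − ICC, so n becomes 60/0.9 = 66.7 up to 60/0.5 = 120. The 3 v 3 interval becomes ±8.7 to ±6.1.

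The direction depends on how plates fall within patients, which Table 3 would not show.

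**The case against.** The strongest reply is that the operative sections are consistent. Bone density is the primary objective, the secondary objectives ask only whether reactions or loosening occur, and the analysis and Table 3 follow from that. Describing secondary safety outcomes is a legitimate choice. This stands. It makes the problem one of over-broad wording in two sentences and limits its weight. It does not remove the problem, because those two sentences state the study's purpose and hypothesis.

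A second reply is that the illustration depends on assumed counts, on the interval chosen and on independence. That also stands for the exact figures. It does not rescue the claim: even no events in either group leaves an interval of several points, with no margin in the available text to judge it by.

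Three stronger readings are tempting and not supported:

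- *That the sponsor never set a margin.* The opening part of the document was not available for review, so a margin there cannot be excluded. The lack of a difference or interval in the analysis section and Table 3 is firmer.
- *That allowing for clustering must widen the interval.* With one plate of each type in a patient it can narrow.
- *That a line-level risk difference would settle both outcomes.* Tissue reaction is recorded at a patient's visit, and the text does not say how edema or inflammation is assigned to one line. If a patient carries both plates, a line-level difference may have no clear meaning.

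**Conclusion.** The mismatch is real. Followed exactly, the plan leaves the non-inferiority claims on tissue reaction and screw loosening without an analysis that could support them. This rests on the text and not on the arithmetic. The figures show only that similar counts can hide a difference of practical size, under assumed event counts and independent lines.

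The weight is modest, because the outcomes are secondary and the formal objectives are already worded descriptively. A reader might infer that correcting this makes the non-inferiority claim sound. It does not: bone density has only a difference test and no margin in the available text, which is a separate and larger problem.

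**What to change.** 1. **Aim and Hypothesis.** Remove tissue reactions and screw loosening from the non-inferiority claim in both places, and state that they are descriptive safety outcomes. If the sponsor prefers to keep the claim, each outcome needs a justified margin and a rule that compares the interval with it.
2. **Table 3.** Add a column *Risk difference (95% CI)* and give the number of patients. Use an interval that allows for several lines per patient, for example a bootstrap that resamples patients. With very few events, show a plain Newcombe interval labelled as ignoring clustering. For tissue reaction, give a line-level difference only where the reaction can be assigned to one plate; otherwise report it by patient.
3. **Time point.** Reconcile the 2-month loosening row in Table 3 with the 3-month CT given in Post-operatively, Assessing Study Results and Table 2.

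The cost is wording in two places, one column, one patient count and one reconciled label, with no extra visits. Assigning tissue reactions to a plate may need one more item on the clinic record if it is not already noted. The downside is a narrower stated claim.

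### The Table 2 footnote defines the bone-density p-value against baseline although every planned test compares the two plates, and no baseline adjustment is planned for the month-3 comparison

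*Combined protocol and SAP*

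**What the plan says.** All statements are in the combined protocol and SAP.

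- **Comparison.** Research Design says that "bone density, local tissue reactions, and screw loosening between these two devices at specific periods will be compared". The Bone Density section says "scores between the two brands will be compared". Data Analysis and Data Presentation says "scores for the dependent variables between groups will be statistically compared using independent t-test or Mann Whitney test", the choice depending on normality. The title of Table 2 sets group I "versus group II (existing benchmark miniplate and screw) at different observation periods".
- **Significance rule.** The asterisk on the p-value column of Table 2 leads to: "Statistically significant difference versus baseline reading if p-value ≤ 0.05". No other threshold is stated. Table 2 has a mean and SD column for each group, a single p-value column, and two rows (immediately after surgery and at three months).
- **Baseline scan.** Post-operatively: "All patients undergo a non-contrast head CT scan on day one postop as a baseline". Assessing Study Results: "subjects will undergo non-contrast head CT scan evaluation immediately after surgery as a baseline". The timing is worded in two ways, but both call this scan the baseline. It is called day-1 HU below.
- **Use of baseline.** No covariate, change score or other adjustment is described.
- **Carry-forward.** Dropout Criteria keeps patients with infection or implant failure in the analysis by LOCF.
- **Unit and size.** Subject Allocation: "Subject is the fracture line found on the patient". A group size of 60 appears only in the header of Table 3.
- **Hypothesis.** Non-inferiority, with no margin.

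**The concern.** The p-value for the primary outcome has two incompatible definitions. The text and the table title ask whether the plates differ. The footnote asks whether HU has changed since surgery. Healing may change HU in both groups whichever plate is used, so a p-value of the second kind says nothing about one plate against the other. Placed in a column headed by the two groups, it could be read as if it did.

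A second, smaller matter concerns precision. The trial collects a baseline HU value for each fracture line but does not plan to use it to sharpen the month-3 comparison. A non-inferiority claim is judged from the confidence interval, so avoidable width matters.

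**Working it through.** **Step 1: the footnote against the rest of the plan.**

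- An independent t-test or Mann-Whitney test between groups cannot yield a versus-baseline result. That would need a paired test, and none is planned.
- A versus-baseline test gives one p-value per group, so two per row. Table 2 has one column.
- The immediate post-operative row is the baseline, so the footnote's definition has no meaning there.

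The contradiction is textual and needs no assumptions.

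**Step 2: what the footnote would report if followed.** Assumptions: 60 independent lines per group (Table 3 header), equal SD at both scans, two-sided 5% level (the plan does not state sidedness), identical plates. The mean gain *g* (in SD) and the day-1 to month-3 correlation *r* are not in the documents, so a range is shown. The paired t-test has 59 df and noncentrality g√60 / √(2(1−r)). For g = 0.5 and r = 0.5 this is 0.5 × 7.746 / 1 = 3.87, giving power 0.968. With independent groups, the chance that both are significant is the square: 0.968² = 0.937.

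| r | g = 0.5, each group | g = 0.5, both | g = 0.2, each group | g = 0.2, both |
|---|---|---|---|---|
| 0 | 0.768 | 0.59 | 0.190 | 0.04 |
| 0.3 | 0.896 | 0.80 | 0.251 | 0.06 |
| 0.5 | 0.968 | 0.94 | 0.332 | 0.11 |
| 0.7 | 0.998 | >0.99 | 0.503 | 0.25 |

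The planned between-group test would be significant in 5% of such trials.

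**Step 3: precision of the month-3 comparison.** Same assumptions, with V = 2/60 and √V = 0.183 SD.

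- Unadjusted: t(0.975, 118) × √V = 1.980 × 0.183 = 0.362 SD.
- ANCOVA: t(0.975, 117) × √(V(1−r²)(1+1/116)).
- Change score: t(0.975, 118) × √(2V(1−r)).

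| r | Unadjusted | ANCOVA | Change score |
|---|---|---|---|
| 0 | 0.362 | 0.363 | 0.511 |
| 0.3 | 0.362 | 0.346 | 0.428 |
| 0.5 | 0.362 | 0.314 | 0.362 |
| 0.7 | 0.362 | 0.259 | 0.280 |

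ANCOVA costs almost nothing at r = 0 and gains as r rises. A change score is worse than no adjustment below r = 0.5.

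**Step 4: the weak point of ANCOVA here.** Day-1 HU is measured after the plate is in place. If the plate itself shifts HU by *a* on both scans, the bias is a (unadjusted), a(1−r) (ANCOVA) and 0 (change score). ANCOVA and the change score have equal mean squared error when a²(1−r)² = 2V(1−r) − V(1−r²) = V(1−r)², so a = √V = 0.183 SD at every r (0.178 to 0.182 after the one-df cost). Above about 0.18 SD the change score does better. At a = 0.2 and r = 0.5, for example, the root mean squared error is 0.183 SD for the change score, 0.188 for ANCOVA and 0.271 unadjusted.

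**Step 5: LOCF.** Only two CTs are scheduled. For a line kept under the LOCF rule without a month-3 scan, the value carried forward is day-1 HU. In an ANCOVA, outcome and covariate would then be equal for that line.

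**The case against.** The strongest reply is that the footnote sits under an empty dummy table. The design, the bone-density section, the named tests and the table title all point to a between-plate comparison, and the named tests cannot produce a within-group result. The likely consequence is a wrong label, not a wrong analysis. This stands, and it limits the weight of the first part.

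On the second part, the primary objective concerns HU after fixation and does not mention change. Under randomisation, with independent lines and no plate effect on day-1 HU, an unadjusted comparison loses only precision, and nothing at r = 0. This also stands: it is an improvement, not an error. The preference for ANCOVA is conditional too, since the documents cannot show that any plate-related HU shift is below 0.18 SD.

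Three stronger readings are tempting, and the documents do not support them:

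- **That identical plates would usually both come out significant under the footnote.** This holds at an assumed 0.5 SD gain but not at 0.2 SD. The documents give no gain, SD or correlation.
- **That day-1 HU plays no part in the month-3 comparison.** Under the LOCF rule it can enter as a carried-forward outcome. What is absent is baseline adjustment.
- **That error rates from several lines in one patient make this point more serious.** Such rates depend on lines per patient and an intraclass correlation, neither of which is given. Clustering matters for how the adjusted model is specified, not for the weight of this point.

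**Conclusion.** The footnote is wrong as written. It contradicts the design, the tests and the title of its own table, and it is the only significance rule for the primary outcome. Because the intended comparison is recoverable from the rest of the text, the realistic harm is a mislabelled result. A reader might infer that the trial will analyse the wrong contrast; the plan does not support that. The size of the distortion if the footnote were followed (both groups significant in 4% to over 99% of trials) rests on assumed gains and correlations.

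The absence of baseline adjustment is a cheap improvement forgone. At 60 independent lines per group and equal SDs, the half-width would fall from 0.362 SD to between 0.346 and 0.259 SD for assumed correlations of 0.3 to 0.7, with no material loss at zero. The sponsor should make both changes. Neither supplies the missing non-inferiority margin.

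**What to change.** 1. **Footnote.** State that the month-3 p-value compares the two plates, and show day-1 HU descriptively without a p-value. Report the between-plate difference with a 95% CI. State that p > 0.05 is not evidence of non-inferiority, which needs a margin the plan does not give.
2. **Primary analysis.** Pre-specify an ANCOVA of month-3 HU on plate, with day-1 HU of the same line as covariate and standard errors clustered by patient. If residuals are clearly non-normal, use a rank-based or patient-level bootstrap version of the adjusted analysis.
3. **Sensitivity analyses.** Name in advance the unadjusted comparison, the change score, and the ANCOVA without lines whose month-3 value is carried forward from day 1. Do not choose among methods from the observed day-1 difference: its standard error, 0.183 SD, is as large as the shift that would matter. If the results disagree, say that a plate-related HU shift cannot be excluded.

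The cost is one footnote, one analysis paragraph and three sensitivity analyses. Both scans are already planned; the only added data item is a patient identifier for each line. The downside is that ANCOVA removes only part of any plate-related shift present on day 1.
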